1 PROTOCOL SUMMARY

1.1 Synopsis

Protocol Title: A Phase 3 Randomized, Open-Label, Clinical Trial to Study the Immunogenicity and Safety of Concomitant and Non-Concomitant Administration of V260 and Inactivated Poliomyelitis Vaccine (IPV) in Chinese Healthy Infants

Short Title: Immunogenicity and safety assessment of concomitant administration of V260 and IPV in Chinese healthy infants

Acronym: V260-074

Hypotheses, Objectives, and Endpoints:

In healthy Chinese infants 48-63 days of age:

Note: Participants randomized to non-concomitant administration of V260 and IPV (staggered-use group) will receive the two study vaccines in a staggered-use schedule.

Objectives	Endpoints
Primary	

Objective: To demonstrate that the immunogenicity of IPV in the concomitant-use group is non-inferior to that in the staggered-use group. 
Hypothesis (H1): The seroconversion percentage at 1 month post dose 3 for each of poliovirus types 1, 2, and 3 in the concomitant-use group is non-inferior to those in the staggered-use group. The statistical criterion for non-inferiority requires that the lower bound of two-sided 95.0% confidence interval for the difference (concomitant-use group minus staggered-use group) in seroconversion percentages be greater than -10% for each poliovirus type.
	
Neutralizing antibody seroconversion to each of poliovirus types 1, 2, and 3

Objectives	Endpoints
Secondary	

 • Objective: To evaluate immune responses to IPV at 1 month post dose 3 in the concomitant-use and staggered-use groups as measured by geometric mean titers (GMTs) of neutralizing antibodies to poliovirus types 1, 2, and 3. • Objective: To evaluate immune responses to IPV at 1 month post dose 3 in the concomitant-use and staggered-use groups as measured by the proportions of participants with neutralizing antibody titer $\geq 1:8$ and $\geq 1:64$ for each of poliovirus types 1, 2, and 3. • Objective: To evaluate the safety of concomitant administration of V260 and IPV based on the proportions of participants experiencing solicited injection-site adverse events (AEs), solicited systemic AEs, and serious AEs (SAEs). 	
 • Neutralizing antibody titer to each of poliovirus types 1, 2, and 3 • Neutralizing antibody responses to each of poliovirus types 1, 2, and 3 • Solicited injection-site AEs (following vaccination of IPV) • Solicited systemic AEs • SAEs

Overall Design:

Study Phase	Phase 3
Primary Purpose	Prevention
Indication	Prevention of rotavirus gastroenteritis in infants and children caused by the serotypes G1, G2, G3, G4, and G9
Population	Chinese healthy infants
Study Type	Interventional
Intervention Model	Parallel This is a single-site study.

Type of Control	Active control (Staggered-use group)
Study Blinding	Unblinded Open-label
Blinding Roles	No Blinding
Estimated Duration of Study	
The Sponsor estimates that the study will require approximately 7 months from the time the first participant signs the informed consent until the last participant’s last study-related telephone call or visit.
 
For purposes of analysis and reporting, the overall study ends when the Sponsor receives the last laboratory result or at the time of final contact with the last participant, whichever comes last.

Number of Participants:

Approximately 400 participants will be enrolled in the study as described in Section 9.9.

Intervention Groups and Duration:

Intervention Groups	
  
 Intervention Group Name	Vaccine	Dose Strength	Dose Frequency	Route of Administration	Use	
   
 Concomitant-Use/Staggered-Use Group	V260 (ROTATEQ®)	2 mL/dose	3 doses	Oral	Experimental	
 
 	IPV (Sabin strain based)	0.5 mL/dose	3 doses	IM	Experimental	
  
	Intervention Group Name	Vaccine	Dose Strength	Dose Frequency	Route of Administration	Use	Concomitant-Use/Staggered-Use Group	V260 (ROTATEQ®)	2 mL/dose	3 doses	Oral	Experimental		IPV (Sabin strain based)	0.5 mL/dose	3 doses	IM	Experimental
	Intervention Group Name	Vaccine	Dose Strength	Dose Frequency	Route of Administration	Use													
	Concomitant-Use/Staggered-Use Group	V260 (ROTATEQ®)	2 mL/dose	3 doses	Oral	Experimental													
	IPV (Sabin strain based)	0.5 mL/dose	3 doses	IM	Experimental														
Abbreviations: IM=Intramuscular; IPV=Inactivated poliomyelitis vaccine.																			
Total Number	Two treatment groups																		
Duration of Participation	
Each participant will participate in the study for approximately 3.5 months from the time the participant’s legally acceptable representative signs the Informed Consent Form through the final contact. After enrollment, each participant will be receiving 3 doses of V260 and IPV in a concomitant-use or staggered-use schedule. After each vaccination of V260 and/or IPV, each participant will be followed for 30 days in the concomitant-use group and for 15 days in the staggered-use group.
																		

Study Governance Committees:

Steering Committee	No
Executive Oversight Committee	No
Data Monitoring Committee	No
Clinical Adjudication Committee	No
Insert Other Oversight Committee	No

Study Accepts Healthy Volunteers: Yes

A list of abbreviations used in this document can be found in Appendix 8.

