1.3 Schedule of Activities

Visit Number		1	2	3	4	5	6	7	8	Notes
Study Month		Day 1	Month 0.5	Month 1	Month 1.5	Month 2	Month 2.5	Month 3	Month 3.5	
Recommended Age (Months)		~1.5	~2	~2.5	~3	~3.5	~4	~4.5	~5	
Concomitant-Use Group	Scheduled Day	Day 1	15 days after V1	15 days after V2	30 days after V2	15 days after V4	30 days after V4	15 days after V6	30 days after V6	
	Visit Window	48-63 days of age	15-21d after V1 (≤84 days of age)	15-21d after V2	30-42d after V2	15-21d after V4	30-42d after V4	15-21d after V6	30-42d after V6	
Staggered-Use Group	Scheduled Day	Day 1	15 days after V1	30 days after V1	30 days after V2	30 days after V3	30 days after V4	30 days after V5	30 days after V6	
	Visit Window	48-63 days of age	15-21d after V1	30-42d after V1 & ≥V2+15d	30-42d after V2 & ≥V3+15d	30-42d after V3 & ≥V4 +15d	30-42d after V4 & ≥V5+15d	30-42d after V5	30-42d after V6	
Administrative Procedures										
Informed Consent		X								Screening procedures may not be performed on the same day of ICF, but screening or rescreening visit should be on the same day as randomization. Screening procedures may be repeated after consultation with the Sponsor.
Assignment of Screening Number		X								
Participant Identification Card		X								
Inclusion/Exclusion Criteria		X								
Medical History		X								
Prior/Concomitant Medications Review		X	X	X	X	X	X	X	X	

Visit Number		1	2	3	4	5	6	7	8	Notes
Study Month		Day 1	Month 0.5	Month 1	Month 1.5	Month 2	Month 2.5	Month 3	Month 3.5	
Recommended Age (Months)		~1.5	~2	~2.5	~3	~3.5	~4	~4.5	~5	
Concomitant-Use Group	Scheduled Day	Day 1	15 days after V1	15 days after V2	30 days after V2	15 days after V4	30 days after V4	15 days after V6	30 days after V6	
	Visit Window	48-63 days of age	15-21d after V1 (≤84 days of age)	15-21d after V2	30-42d after V2	15-21d after V4	30-42d after V4	15-21d after V6	30-42d after V6	
Staggered-Use Group	Scheduled Day	Day 1	15 days after V1	30 days after V1	30 days after V2	30 days after V3	30 days after V4	30 days after V5	30 days after V6	
	Visit Window	48-63 days of age	15-21d after V1	30-42d after V1 & ≥V2+15d	30-42d after V2 & ≥V3+15d	30-42d after V3 & ≥V4+15d	30-42d after V4 & ≥V5+15d	30-42d after V5	30-42d after V6	
Assignment of Treatment/Randomization Number		X								The treatment/randomization number will be randomly assigned by an interactive response technology (IRT) system.

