4 STUDY DESIGN

4.1 Overall Design

This is a randomized, single-site, open-label study of concomitant administration of V260 and IPV in Chinese healthy infants to be conducted in conformance with Good Clinical Practices.

Approximately 400 participants between the ages of 48 days and 63 days will be enrolled and randomly assigned in a 1:1 ratio to receive V260 and IPV in a concomitant (concomitant-use group) or non-concomitant administration (staggered-use group) schedule. Each participant will participate in the study for approximately 3.5 months from the time the participant's legally acceptable representative signs the informed consent through the final contact, including 8 study visits for vaccination, blood sample collection, and safety follow-up.

In the concomitant-use group, an oral dose of V260 (2 mL/dose) will be concomitantly administered (same day) with an intramuscular injection of IPV (0.5 mL/dose) at Visit 2, Visit 4, and Visit 6, respectively. In the staggered-use group, an oral dose of V260 (2mL/dose) will be administered at Visit 1, Visit 3, and Visit 5, respectively, and an intramuscular injection of IPV (0.5 mL/dose) will be administered at Visit 2, Visit 4, and Visit 6, respectively.

In the concomitant-use group, serum samples will be obtained from each participant at Visit 1 prior to vaccination and Visit 8 (1 month post dose 3 of V260 and IPV), respectively. In the staggered-use group, serum samples will be obtained from each participant at Visit 1 prior to vaccination, Visit 7 (1 month post dose 3 of V260), and Visit 8 (1 month post dose 3 of IPV), respectively.

Paper Vaccination Report Card (VRC) will be used by each participant's legally acceptable representative to record participant's daily axillary temperature from Day 1 through Day 7 post each study vaccination; solicited injection-site AEs (erythema, swelling, induration, and pain at the injection-site of IPV) from Day 1 through Day 7 post each vaccination of IPV, and solicited systemic AEs (diarrhea and/or vomiting) from Day 1 through Day 7 post each study vaccination; and any other AEs from Day 1 through Day 15 post each study vaccination in both the concomitant-use and staggered-use groups. In addition, any other AEs from Day 16 through Day 30 post each study vaccination in the concomitant-use group will also be collected on the VRC.

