4.2.1.2 Safety Endpoints

In the concomitant-use group, V260 and IPV will be administered on the same day with an interval of at least 30 days between each vaccination visit, and the safety of the two study vaccines will be collected for 30 days following each vaccination. In the staggered-use group, V260 and IPV will be administered separately with an interval of at least 15 days, therefore the safety of each study vaccine will be collected for 15 days following each vaccination.

Paper VRC will be provided to each participant's legally acceptable representative at each vaccination visit to record participant's daily axillary temperature from Day 1 through Day 7 post each study vaccination; solicited injection-site AEs (erythema, swelling, induration, and pain at the injection-site of IPV) from Day 1 through Day 7 post each vaccination of IPV, and solicited systemic AEs (diarrhea and/or vomiting) from Day 1 through Day 7 post each study vaccination; and any other AEs from Day 1 through Day 15 post study each vaccination in both the concomitant-use and staggered-use groups. In addition, any other AEs from Day 16 through Day 30 post each study vaccination in the concomitant-use group will also be collected on the VRC.

The solicited injection-site AEs will be collected for the safety evaluation of IPV, which is a vaccine to be intramuscularly administered.

Although participants in the concomitant-use group will not receive any study vaccines at Visit 1, VRC will be provided to each participant at Visit 1 to record any reportable safety events from randomization through the first study vaccination (See Section 8.4.1 for safety reporting requirement).

In addition, any SAEs regardless of causality, cancer, overdose, and intussusception (ECI) will be collected during the entire period of study.

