8.3.4 Vaccination Report Card

VRC will be provided to each participant's legally acceptable representative at each study vaccination visit.

Participant's legally acceptable representative will be instructed to record the following information:

- Daily axillary temperature from Day 1 through Day 7 following each study vaccination (Temperature measurement must be recorded on the VRC if a fever is suspected during Day 8 through Day 30 [concomitant-use group] or Day 8 through Day 15 [staggered-use group]);
- Solicited injection-site AEs (erythema, swelling, induration, and pain at the injection-site of IPV) from Day 1 through Day 7 following each vaccination of IPV;
- Solicited systemic AEs (diarrhea and/or vomiting) from Day 1 through Day 7 following each study vaccination;
- Any AEs from Day 1 through Day 30 (concomitant-use group) or from Day 1 through Day 15 (staggered-use group) following each study vaccination;
- Any concomitant medications from Day 1 through Day 15 following each study vaccination (both vaccination groups).
- Any non-study vaccinations from Day 1 through Day 30 (concomitant-use group) or from Day 1 through Day 15 (staggered-use group) following each study vaccination;
- Any medications due to AE during Day 16 through Day 30 following each study vaccination (concomitant-use group only).

Although Visit 1 is not a vaccination visit for participants in the concomitant-use group, VRC will be provided to each participant's legally acceptable representative to record any reportable safety events from randomization through the first study vaccination (See Section 8.4.1 for safety reporting requirement).

At least one telephone contact will be conducted by investigator within 7 days after each visit of VRC distribution to remind each participant's legally acceptable representative to record the VRC and answer their any questions related to VRC.

In the concomitant-use group, the purpose of Visit 3, 5, and 7 is only to review VRCs, so out of windows of these visits will not be reported as a protocol deviation in this vaccination group.

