8.4 Adverse Events, Serious Adverse Events, and Other Reportable Safety Events

The definitions of an AE or SAE, as well as the method of recording, evaluating, and assessing causality of AE and SAE and the procedures for completing and transmitting AE, SAE, and other reportable safety event reports can be found in Appendix 3.

Adverse events, SAEs, and other reportable safety events will be reported by the participant (or, when appropriate, by a caregiver, surrogate, or the participant's legally authorized representative).

The investigator and any designees are responsible for detecting, documenting, and reporting events that meet the definition of an AE or SAE as well as other reportable safety events. Investigators remain responsible for following up AEs, SAEs, and other reportable safety events for outcome according to Section 8.4.3.

The investigator, who is a qualified physician, will assess events that meet the definition of an AE or SAE as well as other reportable safety events with respect to seriousness, intensity/toxicity and causality.

8.4.1 Time Period and Frequency for Collecting AE, SAE, and Other Reportable Safety Event Information

All AEs, SAEs, and other reportable safety events that occur after the consent form is signed but before randomization/allocation must be reported by the investigator if they cause the participant to be excluded from the study, or are the result of a protocol-specified intervention, including but not limited to washout or discontinuation of usual therapy, diet, placebo, or a procedure.

From the time of randomization/allocation through 30 days (concomitant-use group) or 15 days (staggered-use group) following the first vaccination(s) and from the time of any subsequent vaccination(s) through 30 days (concomitant-use group) or 15 days (staggered-use group) thereafter, all AEs, SAEs, and other reportable safety events must be reported by the investigator.

Additionally, SAE (regardless of causality) and intussusception (ECI) at any time outside of the time period specified in the previous paragraph also must be reported immediately to the Sponsor. Other reportable safety events (cancer and overdose) at any time outside of the time period specified in the previous paragraph should also be reported to the Sponsor.

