9.6.2 Statistical Methods for Safety Analyses

Safety and tolerability will be assessed by clinical review of all relevant parameters including AEs and post-vaccination temperature measurements.

An overall assessment of adverse events will be summarized for each group by dose period (dose period is defined in [Table 4](#)) and across all dose periods.

Table 4 Each Group by Dose Period

Dose Period	Concomitant-Use Group (Vaccine administered)	Staggered-Use Group (Vaccine administered)
1	Visit 2 (V260 + IPV)	Visit 1 (V260)
	Visit 3	Visit 2 (IPV)
2	Visit 4 (V260 + IPV)	Visit 3 (V260)
	Visit 5	Visit 4 (IPV)
3	Visit 6 (V260 + IPV)	Visit 5 (V260)
	Visit 7	Visit 6 (IPV)

Summary statistics, counts and percentage without confidence interval, will be provided by group. Proportions of participants with solicited injection-site AEs (following vaccination of IPV), solicited systemic AEs within 7 days following study vaccination will be given. Maximum axillary temperatures recorded on the VRC from Day 1 through Day 7 post-vaccination will be summarized. Table 5 shows the safety endpoints that will be summarized.

Table 5 Analysis Strategy for Safety Parameters

Safety Endpoints	Time Period	Descriptive Statistics
Solicited Injection-Site AEs	Days 1-7 post-vaccination of V260 and IPV in the concomitant-use group, and Days 1-7 post-vaccination of IPV in the staggered-use group, across all dose periods and by dose period	X
Solicited Systemic AEs	Days 1-7 post-vaccination of V260 and IPV in the concomitant-use group, and Days 1-7 post-vaccination of V260 plus Days 1-7 post-vaccination of IPV in the staggered-use group, across all dose periods and by dose period	X
Maximum Axillary Temperature	Days 1-7 post-vaccination of V260 and IPV in the concomitant-use group, and Days 1-7 post-vaccination of V260 plus Days 1-7 post-vaccination of IPV in the staggered-use group, across all dose periods and by dose period	X
Any Injection-Site AEs	Days 1-15 post-vaccination of V260 and IPV in the concomitant-use group, and Days 1-15 post-vaccination of IPV in the staggered-use group, across all dose periods and by dose period	X
Any Systemic AEs	Days 1-30 post-vaccination of V260 and IPV in the concomitant-use group, and Days 1-15 post-vaccination of V260 plus Days 1-15 post-vaccination of IPV in the staggered-use group, across all dose periods and by dose period	X

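### Non-serious AEs on Days 16-30 after the last vaccination (Visit 6) are collected in the concomitant-use group only; extending the staggered-use window after that one visit is a cheap improvement

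*Combined protocol and SAP*

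**What the plan says.** The unequal window appears consistently. In the Synopsis (1.1), after each vaccination "each participant will be followed for 30 days in the concomitant-use group and for 15 days in the staggered-use group". Section 8.4.1 requires all AEs to be reported "from the time of any subsequent vaccination(s) through 30 days (concomitant-use group) or 15 days (staggered-use group) thereafter". The diary instruction in 8.3.4 matches: "Any AEs from Day 1 through Day 30 (concomitant-use group) or from Day 1 through Day 15 (staggered-use group) following each study vaccination". Section 4.1 adds that "any other AEs from Day 16 through Day 30 post each study vaccination in the concomitant-use group will also be collected on the VRC". Table 2 (8.4.1) does not require non-serious AEs to be reported once the follow-up period has ended.

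The reason is in 4.2.1.2. In the staggered-use group the vaccines are given separately "with an interval of at least 15 days, therefore the safety of each study vaccine will be collected for 15 days following each vaccination".

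Visit 6 is the last vaccination in both groups. Under 4.1 the staggered-use group receives V260 at Visits 1, 3 and 5, and "an intramuscular injection of IPV (0.5 mL/dose) will be administered at Visit 2, Visit 4, and Visit 6, respectively". The concomitant-use group receives both vaccines at Visits 2, 4 and 6. The Schedule of Activities (1.3) places Visit 8 at "30-42d after V6" in both groups. It marks diary review and safety follow-up at Visits 7 and 8 without separating the groups.

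In the analysis, Table 5 (9.6.2) summarises any systemic and vaccine-related systemic AEs over Days 1-30 in the concomitant-use group and over "Days 1-15 post-vaccination of V260 plus Days 1-15 post-vaccination of IPV in the staggered-use group". Injection-site AEs are compared over Days 1-15 in both groups. The concomitant-use injection-site AEs over Days 1-30 are summarised separately, with no counterpart.

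**The concern.** The 15-day window suits a schedule in which another vaccine arrives about 15 days later. After Visits 1 to 5 in the staggered-use group that is the case, and the next window opens as the previous one closes. After Visit 6 nothing follows, yet the 15-day limit still applies. In the concomitant-use group the same stretch of time after the same IPV dose is observed for another 15 days.

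What is lost is a comparator. If concomitant-use infants show non-serious systemic, injection-site or vaccine-related events on Days 16-30 after the full course, no staggered-use data at the same age and the same time since IPV can show whether that is background. Section 9.6.2 states an aim of looking for additive safety issues of concomitant against staggered use. The time after Visit 6 is the only stretch in which Days 16-30 after IPV could be compared between the randomised groups without a new study vaccine intervening.

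**Working it through.** **Inputs.** Scheduled visit intervals (1.3); AE windows of 30 and 15 days (1.1, 8.3.4, 8.4.1); vaccination visits (4.1, Table 1); 200 infants per group (9.9.1).

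**1. Schedule check.** With Visit 1 as day 0, Visits 1 to 8 fall on days 0, 15, 30, 45, 60, 75, 90 and 105 in both groups. 105 / 30 = 3.5 months, which reproduces the stated duration of participation.

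**2. Total observation after vaccination.** Concomitant-use: 3 × 30 = 90 days, covering days 15-105. Staggered-use: 6 × 15 = 90 days, covering days 0-90. Within each dose period of Table 4 the comparison is 30 days against 15 + 15. The totals are equal, but scheduled days 91-105 are covered in the concomitant-use group only. In dose period 3 the rows set days 75-105 against days 60-90.

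**3. Days 16-30 after each IPV dose, non-serious AEs, number of days covered.**

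| IPV dose | Scheduled days | Concomitant-use | Staggered-use | Why covered in staggered-use |
|---|---|---|---|---|
| 1 (Visit 2, day 15) | 31-45 | 15 | 15 | V260 window from Visit 3 |
| 2 (Visit 4, day 45) | 61-75 | 15 | 15 | V260 window from Visit 5 |
| 3 (Visit 6, day 75) | 91-105 | 15 | 0 | no later vaccination |

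Over every whole-day schedule that the staggered-use visit windows permit (43,442 schedules), coverage is 3 to 15 days after doses 1 and 2 and always 0 after dose 3. The gap is specific to IPV dose 3. On scheduled days, Days 16-30 after the third V260 dose (day 60, so days 76-90) are covered by the window that opens at Visit 6.

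**4. Size.** 15 of the 30 days after the final dose are not collected in one group: 200 × 15 = 3,000 infant-days, or 170 × 15 = 2,550 with the 170 evaluable infants per group of 9.9.1. Visit 8, at 30-42 days after Visit 6, already lies beyond Day 30.

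**5. Illustration of event counts.** The documents give no rate for late non-serious AEs. Assume 0.2, 0.5 or 1.0 new systemic AEs per 100 infant-days (r = 0.002, 0.005, 0.010 per day). The expected number of 200 infants with at least one event in 15 days is 200 × (1 − exp(−15r)) = 5.9, 14.5 and 27.9. Many would already be counted in the across-period row. Those newly added by the last 15 of 90 days number 200 × (exp(−75r) − exp(−90r)), about 5, 10 and 13. These are gross counts in one slice of time, not differences between groups.

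**6. Effect of extending collection.** Staggered-use coverage of Days 16-30 after Visit 6 rises from 0 to 15 days. Total post-vaccination coverage would then be 105 days against 90, so adding the new days to the existing rows would unbalance them.

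**The case against.** The windows look deliberate. Section 4.2.1.2 can be read as setting one uniform 15-day window per vaccine, and Table 4 with Table 5 then pairs 30 days with 15 + 15 in every dose period. A reader might infer that the systemic AE rows are biased against concomitant use. The documents do not support that: observation is equal per period and overall, so at a constant event rate the expected difference is zero. The age shift behind the equal totals is 15 days, the same as the spread of enrolment ages (48 to 63 days). The counts in step 5 do not measure a bias either, since the staggered-use infants contribute their own 15 days after Visit 1 to the same rows.

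Nor can it be said that late events of every kind are seen in one group only. Serious AEs, intussusception, cancer and overdose are collected throughout in both groups (4.1, 8.4.1), and Table 2 leaves later non-serious AEs optional rather than barring them.

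The proposed comparison is also not perfectly clean. On scheduled days, Days 16-30 after Visit 6 are Days 31-45 after the last V260 dose in the staggered-use group and Days 16-30 in the other. Routine paediatric vaccines are allowed throughout (6.5, 8.1.8.1).

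All of this stands and limits the weight of the point. It does not supply a reason for ending collection at Day 15 after a dose that no study vaccine follows, or a comparator for the concomitant-use data that are collected.

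**Conclusion.** The point holds as a cheap improvement. Non-serious AEs on Days 16-30 after the last vaccination are required in one randomised group and not in the other, because a window explained by vaccine spacing is carried over to a visit where spacing no longer matters. The size is 15 days per infant, about 3,000 infant-days. How many events that represents is unknown, since it depends on a rate the plan does not give.

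The loss is a randomised comparator for late non-serious systemic, injection-site and vaccine-related AEs after the completed course, including the Days 1-30 injection-site summary that now stands alone. The primary endpoint, solicited AEs (Days 1-7), serious AEs, intussusception and the Days 1-15 injection-site comparison are untouched. Safety is summarised by counts and percentages without intervals or tests (9.6.2), so no error rate or power changes. The day counts assume scheduled visit days; the absence of coverage after dose 3 holds on every permitted schedule.

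**What to change.** In 1.1, 4.1, 4.2.1.2, 8.3.4 and 8.4.1, extend AE collection in the staggered-use group to Day 30 after Visit 6 only. Extend the linked diary items in 8.3.4 with it: temperature when fever is suspected, medications given for AEs, and non-study vaccinations. Review the entries at the existing Visit 8.

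Leave the Table 5 rows and their windows unchanged, so that the 90 against 90 day balance is kept. Add one descriptive row set to Table 5, with a matching entry in 9.4.2: any systemic, any injection-site and vaccine-related AEs over Days 1-30 after Visit 6, in both groups. Add a note that time since the last V260 dose differs by about 15 days between the groups.

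The cost is 15 more diary days for about 200 infants, one more row set, and a small protocol and diary amendment, which needs the usual regulatory and ethics review (10.1.1). No visit or blood draw is added.
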